16-May-2011

**LipaCreon® Granules 300 mg Sachet
& LipaCreon® Capsules 150 mg**

Protocol for Special Investigation (All cases)

- Special Investigation (All cases) of LipaCreon in patients with pancreatic exocrine insufficiency due to Cystic Fibrosis -**

Protocol No. : P12-893

LipaCreon® Granules 300 mg Sachet & LipaCreon® Capsules 150 mg
Protocol for Special Investigation (All cases)

- Special Investigation (All cases) of LipaCreon in patients with pancreatic exocrine insufficiency due to Cystic Fibrosis -

1. Objective of registry

The registry aims at collecting the information related to the safety and efficacy in the pancreatic exocrine insufficiency (PEI) patients due to cystic fibrosis (CF) receiving the treatment with LipaCreon in order to obtain the information for the effective and safe use of LipaCreon.

2. Planned number of cases for the registry and justification

Planned number of cases: All the cases

Justification:

The number of enrolled patients in the domestic clinical studies was few, and prompt collection of sufficient information is necessary. And the nationwide CF patient number who was reported during the whole year of 2004, was 13, and the total patients population of CF patient for 10 years from 1995 was 38*. The number of CF patients in Japan is extremely few. From this background, the target of the study is all the cases treated with LipaCreon.

*) The Research Result relating to the intractable pancreatic diseases conducted by MHLW Scientific Research Subsidiary Intractable Disease Research Enterprises during 2005 to 2007: 205-215, 2008

3. Target patients of registry

Patients with PEI attributable to primary disease of CF.

<Indications>

Replacement of pancreatic digestive enzymes in PEI

<Precautions for use related to indications>

Administer LipaCreon to patients with having symptoms of steatorrhea or other symptomatology due to PEI because of underlying diseases of chronic pancreatitis (CP) during non-compensatory period, pancreatectomy (PY) and pancreatic CF, etc.

<Contraindication>

- (1) Patients with a history of hypersensitivity to the ingredient of LipaCreon.
- (2) Patients with a history of hypersensitivity to porcine protein.

4. Dosage & administration method

Usually, 600 mg/meal of LipaCreon should be administered t.i.d. orally, immediately after meal.

In addition, the dose should be adjusted as needed based on patient's condition.

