9	Criteria for exclusion from the effectiveness analysis	
 ▪ Cannot be determined: Patients in whom all of “nutritional endpoints, symptoms related to exocrine pancreatic insufficiency, and degree of overall improvement” after the start date of treatment are unknown/unspecified or cannot be determined
10	Patients excluded from the effectiveness analysis	Patients meeting the criteria for exclusion from the effectiveness analysis among the patients included in the safety analysis

No	Definition name	Description
11	Patients included in the effectiveness analysis	Patients not meeting the criteria for exclusion from the effectiveness analysis among the patients included in the safety analysis
12	Patients not completing the 52-week treatment	Patients who have discontinued treatment before Week 48 among the patients included in the effectiveness analysis
13	Patients included in the effectiveness analysis (patients completing the 52-week treatment)	Patients who have completed the 52-week treatment among the patients included in the effectiveness analysis

LPC02T will target all patients, even those who have transferred to another department or hospital. If the same patient is registered multiple times at different institutions or departments, overlapped registrations will be linked to each other and counted as “1 patient.” All case report forms/follow-up case report forms collected at the individual departments/institutions will be regarded as separate volumes for the same patient and the data included in the case report forms will be handled accordingly. Evaluation time points will be calculated with the first “start date of treatment” being deemed as the starting point.

Details will be determined depending on the actual case.

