2.2. Definitions of Analysis Items

No	Definition name	Description
1	Start date of treatment with Lipacreon (start date of the observation period)	Earliest start date of treatment recorded in the “2. Status of Use of Lipacreon” column
2	End date of treatment with Lipacreon (safety)	Latest end date of treatment recorded in the “2. Status of Use of Lipacreon” column However, if there is a record with no date because the end date of treatment is “Ongoing,” “March 31, 2018” will be deemed as the end date of treatment with Lipacreon.
3	End date of treatment with Lipacreon (effectiveness rate)	With the start date of treatment being deemed as Day 1, Day 364 will be determined to be the end date of treatment. However, if the duration of treatment with Lipacreon is fewer than 364 days, the latest end date of treatment recorded in the “2. Status of Use of Lipacreon” column will be deemed as the end date of treatment.
4	Mean daily dose (safety)	Total dose (mg)/Duration of treatment (not including any rest periods) (mg/day)
5	Mean daily dose (effectiveness rate)	With the start date of treatment with Lipacreon being deemed as Day 1, the mean daily dose will be calculated by dividing the total dose (mg) until Day 364 by 364 days (or the number of days of any rest periods subtracted from 364)
6	Duration of use of Lipacreon (safety)	The actual number of days Lipacreon was administered will be calculated. Any rest period will not be included and “Treatment compliance” will not be taken into account.
7	Duration of use of Lipacreon (effectiveness rate)	With the start date of treatment with Lipacreon being deemed as Day 1, the actual number of days Lipacreon was administered until Day 364 will be calculated. Any rest period will not be included and “Treatment compliance” will not be taken into account.

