36	Initial daily dose (mg/day)	The initial daily dose will be determined based on the daily dose on the start date of treatment with Lipacreen. <900, 900, >900 and <1800, 1800, >1800, unknown/unspecified

No	Patient demographic factor	Description
37	Mean daily dose (safety) (mg/day)	
The mean daily dose will be determined based on the mean daily dose (safety). <900, 900, >900 and <1800, 1800, >1800, unknown/unspecified
 
The mean daily dose for each dose observation period will be determined based on the mean daily doses during the individual periods shown below.
 
Dose observation periods:
 
 At the start of treatment: Day 1 At Week 2: Day 2 to Day 14 At Week 4: Day 15 to Day 28 At Week 8: Day 29 to Day 56 At Week 16: Day 57 to Day 112 At Week 24: Day 113 to Day 168 At Week 32: Day 169 to Day 224 At Week 40: Day 225 to Day 280 At Week 48: Day 281 to Day 336 At Week 52: Day 337 to Day 364 At Year 2: Day 365 to Day 728 At Year 3: Day 729 to Day 1092 At Year 4: Day 1093 to Day 1456 At Year 5: Day 1457 to Day 1820 At Year 6: Day 1821 to Day 2184 At Year 7: Day 2185 to Day 2400

No	Indicator of treatment status	Description
38	Mean daily dose (effectiveness rate) (mg/day)	
The mean daily dose will be determined based on the mean daily dose (effectiveness rate). <900, 900, >900 and <1800, 1800, >1800, unknown/unspecified
 
The mean daily dose for each dose observation period will be determined based on the mean daily doses during the individual periods shown below.
 
Dose observation periods:
 
 At the start of treatment: Day 1 At Week 2: Day 2 to Day 14 At Week 4: Day 15 to Day 28 At Week 8: Day 29 to Day 56 At Week 16: Day 57 to Day 112 At Week 24: Day 113 to Day 168 At Week 32: Day 169 to Day 224 At Week 40: Day 225 to Day 280 At Week 48: Day 281 to Day 336 At Week 52: Day 337 to Day 364

No	Indicator of treatment status	Description
39	Maximum daily dose (safety) (mg/day)	
The maximum daily dose will be determined based on the maximum value of the daily dose during the duration of use of Lipacreon (safety). <900, 900, >900 and <1800, 1800, >1800, unknown/unspecified
 
In the summarization for the occurrence status of adverse events and adverse drug reactions, the maximum daily dose in a patient experiencing an adverse event or adverse drug reaction will be determined based on the maximum daily dose until the time of initial onset of the event.

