3.4. Handling of Adverse Events

In the summarization of the number of adverse events (adverse drug reactions) by PT, if the same patient experiences any adverse event (adverse drug reaction) of the same PT multiple times, each event will be counted once (number of events basis). In the summarization of the number of patients with adverse events (adverse drug reactions) by SOC or PT, if the same patient experiences any adverse event (adverse drug reaction) of the same SOC or PT multiple times, the patient will be counted once (number of patients basis).

Adverse events (adverse drug reactions) will be summarized using the “ICH International Medical Dictionary for Regulatory Activities Japanese Version (MedDRA/J)” according to the notification concerning the “ICH International Medical Dictionary for Regulatory Activities Japanese Version (MedDRA/J)” (Notification No. 0325001 of the Safety Division, Pharmaceutical and Food Safety Bureau, MHLW, and Notification No. 0325032 of the Evaluation and Licensing Division, Pharmaceutical and Food Safety Bureau, MHLW, dated March 25, 2004).

The version of the MedDRA/J used for summarization and analysis will be defined in the written statistical analysis specification.

The procedure for summarization and analysis through grouping of MedDRA terms by SOC is as follows:

- According to the LLT entered (coded) in the database, the MedDRA table of the above version will be referenced to follow the link for each adverse event and combine the LLT with the information on “PT-SOC” of the version.

- Adverse event terms will be output in the ascending order of the SOC internationally agreed order-PT codes.

3.5. Rules about Calculation Methods for Individual Items, Units, and Number of Digits Displayed

Item	Unit	Digits displayed	Calculation method, etc.
Calculation of durations (duration to discontinuation, duration to onset of adverse drug reaction, duration of treatment)	day	1	End date – Start date + 1 (including the start date) 1 year = 52 weeks = 364 days
Age	years old	1	INT ([Start date of treatment with Lipacreon – Date of birth + 1)/365.25)
P-value	-	0.001	All numbers after the third decimal place will be disregarded.
Incidence	-	0.01	
Effectiveness rate	-	0.1	Evaluation of the degree of overall improvement: Number of improved patients/(No. of improved patients + No. of unchanged patients + No. of deteriorated patients) × 100

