4.1.1.2. Breakdown of discontinued patients

For patients with available case report forms, patients included in the safety analysis, patients included in the effectiveness analysis, and patients included in the effectiveness analysis (patients completing the 52-week treatment), the number of the individual patients will be presented by reason for discontinuation and observation period category (Table 1.1.2).

No	Item name	Description
1	Observation period category	≤ 28 days, >28 days and ≤ 56 days, >56 days and ≤ 112 days, >112 days and ≤ 168 days, >168 days and ≤ 224 days, >224 days and ≤ 280 days, >280 days and ≤ 364 days, >364 days and ≤ 728 days, >728 days and ≤ 1092 days, >1092 days and ≤ 1456 days, >1456 days and ≤ 1820 days, >1820 days and ≤ 2184 days, >2184 days and ≤ 2400 days

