4.1.1.3. Breakdown of patient composition

The following will be presented: the number of institutions surveyed, the number of patients registered in the survey, the number of patients with available case report forms, the number of patients with no available case report forms, the number of patients included in the safety analysis, the number of patients excluded from the safety analysis, the number of patients included in the effectiveness analysis, the number of patients excluded from the effectiveness analysis, the number of patients included in the effectiveness analysis (patients completing the 52-week treatment), and the number of patients not completing the 52-week treatment. For patients excluded from the safety analysis and patients excluded from the effectiveness analysis, the number of the individual patients will be presented by reason for exclusion (Figure 1.1.3.1).

In addition, the number of patients with available case report forms will be presented by separate volume (Figure 1.1.3.2).

For patients with multiple reasons for exclusion among the patients excluded from the safety analysis or patients excluded from the effectiveness analysis, a list of patients will be prepared (Table 1.1.3.1, Table 1.1.3.2).

For patients excluded from the safety analysis, lists of reported adverse events will be prepared by SOC, PT, seriousness, and presence/absence of relationship (Table 1.1.3.3).

For discontinued patients, a list of patients will be prepared by survey-participating institution (Table 1.1.3.4).

No	Item name	Contents to be displayed
1	Survey-participating institution	-
2	Department name	-
3	Patient number	-
4	Age	Actual value
5	Sex	Male, female
6	Start date of treatment	-
7	End date of treatment	-
8	Number of days from the start of treatment to discontinuation	-
9	Reason for discontinuation	Occurrence of an adverse event, unsatisfactory therapeutic effect, patient's refusal to receive Lipacreon, no visit, worsening of cystic fibrosis of the pancreas, other For "other," a specific reason for discontinuation will be presented.
10	Name of the adverse event as the reason for discontinuation	-
11	Seriousness	Non-serious, serious
12	Causal relationship with Lipacreon	Related, possibly related, unrelated, cannot be determined
13	Outcome	Resolved, resolving, not resolved, sequelae, fatal, unknown
14	Date of onset	-
15	Number of days to onset	-
16	Inclusion/exclusion of patient in the safety analysis	Included, excluded

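### SAP 2.1 ends non-completion at Week 48 but starts completion at Week 52, so read literally a patient stopping on Days 336-363 is in neither set

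*SAP*

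**What the plan says.** SAP 2.1 splits the effectiveness set (No. 11) by whether the first year of treatment was finished.

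- No. 12, the non-completers: "Patients who have discontinued treatment before Week 48 among the patients included in the effectiveness analysis".
- No. 13, the completers: "Patients who have completed the 52-week treatment among the patients included in the effectiveness analysis". No day count or tolerance is given.

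Other parts of the SAP fix the length of 52 weeks. Section 3.5 states "1 year = 52 weeks = 364 days". Section 2.2 No. 3, on the treatment period for the effectiveness rate, says "Day 364 will be determined to be the end date of treatment" unless treatment was shorter. The dose periods in section 2.3 place the end of Week 48 at Day 336: "At Week 48: Day 281 to Day 336".

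Section 3.6 sets the Week 52 assessment window at Day 364 plus or minus 28 days. This window governs evaluation dates. It does not mention completion of treatment.

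Section 4.1.1.3 puts the effectiveness set, the completers "and the number of patients not completing the 52-week treatment" into the patient flow diagram (Figure 1.1.3.1), with no third category. Sections 4.3.1 to 4.3.3 run the effectiveness outputs twice, once in No. 11 and once in the completers.

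**The concern.** Two sets that look like the halves of one parent set use different cut-points. The SAP's other pairs do not: Nos. 7 and 8 (safety) and Nos. 10 and 11 (effectiveness) are each written as meeting or not meeting a single criterion. Only Nos. 12 and 13 leave room between them.

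Two things are at stake.

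1. The patient flow. If anyone stops between the two cut-points, the two counts in Figure 1.1.3.1 sum to less than the effectiveness set, and the figure has no box for the difference.
2. The completer tables. A patient who stops on, say, Day 350 and is assessed that day has a value inside the Week 52 window. Section 3.6 uses the discontinuation time point only for values that fit none of the windows listed above it, so this is a Week 52 value. It enters Table 3.1.1.1. Read literally, it does not enter the completer counterpart, Table 3.1.1.2, and the same applies to Tables 3.1.2.2, 3.2.1.2 and 3.3.1.2.

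The disease is so rare in Japan that the protocol surveys every treated case. One patient more or less in a set is therefore visible in the percentages.

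**Working it through.** The documents give no figure on this point to reproduce. The check is a day count, followed by a rough scale.

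**Inputs from the documents**

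- Non-completer: stopped before Week 48 (SAP 2.1 No. 12).
- Completer: finished 52 weeks (SAP 2.1 No. 13), which is 364 days (SAP 3.5; also the end of treatment in SAP 2.2 No. 3).
- Week 52 window: Day 364 ± 28 (SAP 3.6).

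**Day count**

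- Week 48 = 48 × 7 = Day 336. Week 52 = 52 × 7 = Day 364.
- Week 52 window: 364 − 28 = Day 336 to 364 + 28 = Day 392.
- Stop days that are neither before Day 336 nor at Day 364 or later: Days 336 to 363, which is 363 − 336 + 1 = 28 days.

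The phrase about Week 48 can be read in other ways, so the count was repeated for each:

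| Before Week 48 means before | Gap if completion = Day 364 | Gap if completion = Day 336 |
|---|---|---|
| Day 336 (end of week 48) | 28 days (336-363) | 0 days |
| Day 330 (first day of week 48, 47 × 7 + 1) | 34 days (330-363) | 6 days (330-335) |
| Day 281 (first day of the SAP's Week 48 dose period) | 83 days (281-363) | 55 days (281-335) |

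Of the readings tabulated, the gap closes only when both definitions use Day 336. The SAP does not say that they do.

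**Can the planned summary tables identify these patients?** Table 1.1.2 pools stops in one category, ">280 days and ≤ 364 days". The duration category from 337 to 364 days (SAP 2.3 No. 25) mixes them with patients treated to Day 364. Neither isolates Days 336-363.

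**Scale (assumed)**

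The protocol gives no survey size. The only counts are national: 13 patients reported in 2004, and "the total patients population of CF patient for 10 years from 1995 was 38". I use 38 as a stand-in for the effectiveness set. I assume that 10%, 20% or 30% stop in the first year, with stops spread evenly over 364 days.

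- Share of first-year stops falling in the gap: 28/364 = 7.7%.
- Chance p that a given patient stops in the gap: 0.10 × 0.0769 = 0.0077; 0.20 × 0.0769 = 0.0154; 0.30 × 0.0769 = 0.0231.
- Expected patients, 38 × p: 0.29; 0.58; 0.88.
- Chance of at least one, 1 − (1 − p)^38: 25%; 45%; 59%.
- Weight of one patient in a set of 38: 1/38 = 2.6 percentage points.

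With 13 patients instead of 38, the expected number is 0.10 to 0.30, and the chance of at least one is about 10% to 26%.

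**The case against.** The strongest reply is that the gap is only apparent. The labels of Nos. 12 and 13 are complements, and the SAP's other pairs are true complements. Day 336 is exactly where the Week 52 window opens. On this view No. 12 defines non-completion with a deliberate four-week tolerance, No. 13 is the remainder, and the gap is 0 days. This reading is plausible and may well be what was meant. But it is an inference: the SAP does not tie Week 48 to the assessment window, and No. 13 as worded asks for 52 weeks. The remark in section 2.1 that details will be settled case by case follows the text on duplicate registrations. Stretching it to cover this point would mean deciding set membership with the data in view.

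Three further replies stand.

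- A reader might infer that Week 52 data are lost from the analysis. They are not. The patient stays in No. 11 and so in Tables 3.1.1.1, 3.1.2.1, 3.2.1.1 and 3.3.1.1. At most the value is missing from the second, completer run.
- A reader might infer that the patient flow is certain not to add up. It fails only if someone stops in the gap. In the middle scenario above (38 patients, 20% stopping), no such patient is slightly more likely than one or more.
- Any such patient can be traced. Table 1.1.3.4 lists days to discontinuation for each discontinued patient, and Table 5.2.1.1 gives the discontinuation date. These listings limit the harm, but they do not say which set the patient belongs to.

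**Conclusion.** The point holds on the text as written. Nos. 12 and 13 do not divide No. 11 between them, and a patient stopping on Days 336-363 is assigned to neither. The consequence is conditional and limited: counts in Figure 1.1.3.1 that may not sum, and Week 52 values that may be absent from the completer tables while remaining in the full effectiveness tables.

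The 28-day gap follows directly from the documents under the most natural reading of Week 48. The patient numbers do not. About 0.3 to 0.9 patients, and a 25-59% chance of at least one, rest on an assumed 38 patients, an assumed 10-30% first-year stopping rate and an even spread of stops.

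The documents do not support saying that any main effectiveness result depends on this. It should still be corrected, because it is a set definition that leaves some patients unassigned, the set feeds a second run of the effectiveness outputs, and the correction is nearly free.

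**What to change.** Redefine No. 13 as all patients in No. 11 who do not meet No. 12. Give the cut-off as a day number used by both definitions, and state that Nos. 12 and 13 sum to No. 11. Say also whether the days are calendar days from the first start of treatment or exclude rest periods. The section 2.2 duration items exclude rest periods, the section 3.6 windows count days from the start date, and Nos. 12 and 13 are silent.

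Either cut-off makes the counts add up, but they are not equivalent:

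- **Day 336 (preferred).** Non-completers stopped before Day 336, and completers are everyone else in No. 11. This matches the opening of the Week 52 window and keeps those Week 52 values in the completer tables. The small downside is that a completer may then have had only 48 weeks of treatment, which the footnotes of the completer tables and Figure 1.1.3.1 must say.
- **Day 364.** Non-completers stopped before Day 364. The label is then literally true, but patients stopping on Days 336-363 remain outside the completer tables even when they have a valid Week 52 value.

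The cost is a few lines of SAP wording and a footnote. It needs no new data and does not change how patients are managed.

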2.2. Definitions of Analysis Items

No	Definition name	Description
1	Start date of treatment with Lipacreon (start date of the observation period)	Earliest start date of treatment recorded in the “2. Status of Use of Lipacreon” column
2	End date of treatment with Lipacreon (safety)	Latest end date of treatment recorded in the “2. Status of Use of Lipacreon” column However, if there is a record with no date because the end date of treatment is “Ongoing,” “March 31, 2018” will be deemed as the end date of treatment with Lipacreon.
3	End date of treatment with Lipacreon (effectiveness rate)	With the start date of treatment being deemed as Day 1, Day 364 will be determined to be the end date of treatment. However, if the duration of treatment with Lipacreon is fewer than 364 days, the latest end date of treatment recorded in the “2. Status of Use of Lipacreon” column will be deemed as the end date of treatment.
4	Mean daily dose (safety)	Total dose (mg)/Duration of treatment (not including any rest periods) (mg/day)
5	Mean daily dose (effectiveness rate)	With the start date of treatment with Lipacreon being deemed as Day 1, the mean daily dose will be calculated by dividing the total dose (mg) until Day 364 by 364 days (or the number of days of any rest periods subtracted from 364)
6	Duration of use of Lipacreon (safety)	The actual number of days Lipacreon was administered will be calculated. Any rest period will not be included and “Treatment compliance” will not be taken into account.
7	Duration of use of Lipacreon (effectiveness rate)	With the start date of treatment with Lipacreon being deemed as Day 1, the actual number of days Lipacreon was administered until Day 364 will be calculated. Any rest period will not be included and “Treatment compliance” will not be taken into account.
8	Concomitant drugs (safety)	Among the drugs recorded in the “3. Status of Use of Concomitant Drugs” column, any drug that has a recorded duration of use, meets the condition (its start date of use is between the start date of treatment with Lipacreon and the end date of treatment with Lipacreon [safety]) (including its continued use at the time of the start of treatment with Lipacreon), and is used for reasons other than “treatment of any adverse event” will be deemed as a concomitant drug. (This is because it will not be possible to obtain correct results if any drug used to treat an adverse event is included when determining whether any difference in the incidence of adverse drug reactions exists between when any concomitant drug is used or not used)
9	Concomitant drugs (effectiveness rate)	Among the drugs recorded in the “3. Status of Use of Concomitant Drugs” column, any drug that has a recorded duration of use, meets the condition (its start date of use is between the start date of treatment with Lipacreon and the end date of treatment with Lipacreon [effectiveness rate]) (including its continued use at the time of the start of treatment with Lipacreon), and is used for reasons other than “treatment of any adverse event” will be deemed as a concomitant drug. (This is because it will not be possible to obtain correct results if any drug used to treat an adverse event is included when determining whether any difference in the incidence of adverse drug reactions exists between when any concomitant drug is used or not used)

No	Definition name	Description
10	Digestive enzyme preparations	Drugs corresponding to the following codes: Codes that begin with 2331 or 2339 *Excluding the code corresponding to Lipacreon
11	Adverse events	All events recorded in the “4. Adverse Event” column
12	Relationship with Lipacreon	The relationship with Lipacreon will be assessed as “Related” if the “causal relationship with Lipacreon” is “related,” “possibly related,” or “cannot be determined,” and as “Not related” if the “causal relationship with Lipacreon” is “unrelated.”
13	Adverse drug reactions	Among adverse events, any event whose “causal relationship with Lipacreon” is assessed as “Related” If the same adverse event (preferred term [PT]) occurs repeatedly and is recorded multiple times, any event related with Lipacreon will be counted.
14	Serious adverse events	Among adverse events, any event whose “causal relationship with Lipacreon” is recorded and whose “seriousness” is “Serious” If the same adverse event (PT) occurs repeatedly and is recorded multiple times, any serious event will be counted.

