24	Duration of treatment (safety) (excluding any rest period)	≤28 days, >28 days and ≤56 days, >56 days and ≤84 days, >84 days and ≤168 days, >168 days and ≤252 days, >252 days and ≤336 days, >336 days and ≤364 days, >364 days and ≤2 years, >2 years and ≤3 years, >3 years and ≤4 years, >4 years and ≤5 years, >5 years and ≤6 years, >6 years and ≤7 years, unknown/unspecified In the summarization for the occurrence status of adverse events and adverse drug reactions, the duration of treatment in a patient experiencing an adverse event or adverse drug reaction will be determined based on the number of days until the initial onset date of the event (including the date of onset).
25	Duration of treatment (effectiveness rate) (excluding any rest period)	≤28 days, >28 days and ≤56 days, >56 days and ≤84 days, >84 days and ≤168 days, >168 days and ≤252 days, >252 days and ≤336 days, >336 days and ≤364 days, unknown/unspecified
26	Duration of treatment (safety) (excluding any rest period)	Actual value
27	Duration of treatment (effectiveness rate) (excluding any rest period)	Actual value until Day 364 excluding any rest periods
28	Total dose (safety)	Categories will be determined based on the distribution of actual data.
No	Indicator of treatment status	Description
29	Total dose (effectiveness rate)	Categories will be determined based on the distribution of actual data.
30	Total dose (safety)	Actual value of the total dose during the duration of use of Lipacreen (safety)
31	Total dose (effectiveness rate)	Actual value of the total dose during the duration of use of Lipacreen (effectiveness rate)
32	Reason for dose change (safety) (multiple answers are allowed)	Reason for dose change during the duration of use of Lipacreen (safety) Unsatisfactory therapeutic effect, occurrence of an adverse event, patient's request, other
33	Reason for dose change (effectiveness rate) (multiple answers are allowed)	Reason for dose change during the duration of use of Lipacreen (effectiveness rate) Unsatisfactory therapeutic effect, occurrence of an adverse event, patient's request, other
34	Treatment compliance (safety) (multiple answers are allowed)	Treatment compliance during the duration of use of Lipacreen (safety) Good, half, poor, unknown/unspecified
35	Treatment compliance (effectiveness rate) (multiple answers are allowed)	Treatment compliance during the duration of use of Lipacreen (effectiveness rate) Good, half, poor, unknown/unspecified

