4.1.3.1. Distribution of patients by indicator of treatment status

For patients with available case report forms, patients included in the safety analysis, patients included in the effectiveness analysis, and patients included in the effectiveness analysis (patients completing the 52-week treatment), the number and percentage of the individual patients will be calculated for each of the indicators of treatment status defined in Section 2.3. In addition, for the number of days of treatment (excluding any rest period) and the total dose, summary statistics will be calculated (Table 1.3.1).

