4.2.2.2. Changes in the dose

For patients included in the safety analysis, the number and percentage of patients by dose increase and decrease pattern will be calculated (Table 2.2.2).

No	Item name	Description
1	Dose increase and decrease pattern	
Not changed, increased, decreased, other Not changed: Certain daily dose throughout the duration of treatment with Lipacreon excluding any rest period Increased: Initial daily dose = Lowest daily dose < Maximum daily dose = Last daily dose Decreased: Initial daily dose = Maximum daily dose > Lowest daily dose = Last daily dose Other: Dose increase and decrease patterns other than the above
 
Initial daily dose: Daily dose at the start of treatment with Lipacreon Minimum daily dose: Lowest daily dose during the duration of treatment with Lipacreon excluding any rest period Maximum daily dose: Highest daily dose during the duration of treatment with Lipacreon excluding any rest period Last daily dose: Daily dose at the end of treatment with Lipacreon

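### Mean daily dose (effectiveness rate) keeps a divisor of 364 less rest days when treatment ends before Day 364, so early stoppers get too low a dose

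*SAP*

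**What the plan says.** SAP 2.2 item 5 forms the mean daily dose (effectiveness rate) by "dividing the total dose (mg) until Day 364 by 364 days (or the number of days of any rest periods subtracted from 364". It has no clause for treatment that stops earlier.

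The definitions around it do allow for an early stop:

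- 2.2 item 3 sets the end of treatment (effectiveness rate) at Day 364, but "if the duration of treatment with Lipacreon is fewer than 364 days, the latest end date of treatment recorded" is used instead.
- 2.2 item 4, the safety counterpart of item 5, is "Total dose (mg)/Duration of treatment (not including any rest periods) (mg/day".
- 2.2 item 7 defines duration of use (effectiveness rate): "the actual number of days Lipacreon was administered until Day 364 will be calculated", leaving out rest periods.
- 2.3 item 27 reports that duration as "Actual value until Day 364 excluding any rest periods".
- 2.3 item 31 defines the total dose as "Actual value of the total dose during the duration of use of Lipacreen (effectiveness rate", that is, over the item 7 days.

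The item 5 result is banded in 2.3 item 38 (below 900, 900, between 900 and 1800, 1800, above 1800 mg/day). It is tabulated under 4.1.3.1 in Table 1.3.1, where "for the number of days of treatment (excluding any rest period) and the total dose, summary statistics will be calculated" as well. Under 4.3.1.2 it is tested as a factor for effectiveness in Tables 3.1.2.1 and 3.1.2.2. By 2.1 items 11 and 12, patients who stop early remain in the effectiveness analysis set.

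**The concern.** For an early stopper the numerator of item 5 ends at the last dose, while the divisor runs on to Day 364. The days after stopping count as days at zero dose. The variable then measures dose multiplied by the fraction of the year treated, and it disagrees with the total dose and duration that the SAP defines for the same patient and period.

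Two outputs are at stake. The mean-dose row of Table 1.3.1 is misstated for every early stopper. In Table 3.1.2.1 the dose factor becomes partly a marker of early stopping. If early stoppers are rated differently from others, and their rating enters the test, a dose-effectiveness association can appear among patients who all took the same daily dose. The rating could be from Week 24 (window Day 168 ± 28, so Day 140 to 196), from discontinuation or last evaluation, or from Week 52 (window opening on Day 336). SAP 4.3.1.2 does not say which is used, and the direction of any bias depends on the ratings.

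**Working it through.** The SAP prints no mean-dose figure to reproduce, so the check applies its definitions to worked cases.

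**Inputs.** The divisor is from 2.2 item 5, the comparator from 2.2 item 4, and the treated days from 2.2 item 7. The dose of 1800 mg/day is the usual daily dosage in protocol section 4. The last treatment day d and the rest days r are assumed, because the documents give no values.

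**Formulas.** Let T be the total dose up to Day 364, with d ≤ 364.

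- Item 5: T/(364 − r)
- Dose per treated day (item 4 form, item 7 days): T/(d − r)
- Ratio of the first to the second: (d − r)/(364 − r), which is 1 only at d = 364

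**Constant 1800 mg/day, r = 0.** Item 5 gives 1800 × d/364, and the shortfall is 1 − d/364.

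| Last day d | Item 5 (mg/day) | Shortfall | Band |
|---|---|---|---|
| 28 | 138.5 | 92.3% | below 900 |
| 84 | 415.4 | 76.9% | below 900 |
| 140 | 692.3 | 61.5% | below 900 |
| 168 | 830.8 | 53.8% | below 900 |
| 196 | 969.2 | 46.2% | 900 to 1800 |
| 252 | 1246.2 | 30.8% | 900 to 1800 |
| 337 | 1666.5 | 7.4% | 900 to 1800 |
| 363 | 1795.1 | 0.3% | 900 to 1800 |
| 364 | 1800.0 | 0 | 1800 |

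Dividing by treated days gives 1800 in every row. The band is below 900 for any stop up to Day 181 (895.1), exactly 900 at Day 182, and between 900 and 1800 from Day 183 (904.9) to Day 363.

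**With rest days.** For d = 168 and r = 14, T = 1800 × 154 = 277,200 mg. Item 5 gives 277,200/350 = 792.0 mg/day; item 4 gives 277,200/154 = 1800.

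**Consistency within Table 1.3.1.** For d = 168 and r = 0, the patient contributes 302,400 mg and 168 days, and 302,400/168 = 1800. Item 5 gives 302,400/364 = 830.8 for the same patient.

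**Check of the correction.** Take a patient treated to Day 400 at 1800 mg/day with 50 rest days before Day 364. The dose to Day 364 is 314 × 1800 = 565,200 mg, and the item 7 duration is 314 days. The result is 565,200/314 = 1800, the same as the current item 5 (364 − 50 = 314). The numerator must also stop at Day 364: carried to Day 400 it would be 350 × 1800 = 630,000 mg, and 630,000/314 = 2006.

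**The case against.** The strongest reply is that the SAP never defines a rest period. If every undosed day up to Day 364 counts as rest, including days after permanent discontinuation, the divisor becomes 364 − r − (364 − d) = d − r and the error disappears. Items 3 and 7 suggest that the authors had treated time in mind. On this view item 5 is loosely worded and not wrong.

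That reading fits the text poorly. Section 4.2.2.2 describes an unchanged dose as "Certain daily dose throughout the duration of treatment with Lipacreon excluding any rest period", which places rest periods inside the duration of treatment. Item 3 ends treatment at the last recorded date, and 4.2.1.3 lists suspension and discontinuation as separate actions. If it was the intended meaning, the sentence still needs rewording, because a programmer following it would divide by 364 − r.

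Other points on that side stand and limit the importance:

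- Mean daily dose (safety) appears in Table 1.3.1 for the same analysis sets and is correct for anyone who stops before Day 364. Individual doses and dates are listed in Table 5.2.1.1. The true dose is therefore recoverable, although 4.3.1.2 calls for the effectiveness-rate version in the factor tests.
- Table 1.3.1 shows group counts and summary statistics, so the conflict within one patient would not be visible there.
- The factor tests are exploratory and unadjusted for multiplicity (3.2). The population is very small: protocol section 2 cites 13 patients reported in 2004 and 38 over ten years. Five dose bands would support little inference even with a correct divisor.
- Patients stopping on Day 28 or 84 have no rating in the Week 24 window and enter the test only if a discontinuation or last rating is used.
- Table 3.1.2.2 is touched only if stops on Days 337 to 363 count as completing 52 weeks, which 2.1 items 12 and 13 leave open. The shift there is at most 7.4%, and the change of band mostly reflects 1800 being an exact-value category.

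**Conclusion.** Item 5 is wrong as written and should be fixed. It understates the mean daily dose of anyone whose treatment ends before Day 364 by the factor (d − r)/(364 − r). For a stop inside the Week 24 rating window, with no rest days, the shortfall is 62% to 46%. For stops on Days 337 to 363 it is negligible to small.

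The conclusion assumes that days after the last dose are not rest days, which is the reading the rest of the SAP supports. The dose and stop days are illustrative, and the number of patients affected cannot be computed.

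The scope is narrow. Initial, maximum and last daily dose, the per-period means, mean daily dose (safety), the overall effectiveness rate, and the nutritional, symptom and safety results are all unaffected.

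**What to change.** Reword SAP 2.2 item 5 so that the mean daily dose (effectiveness rate) is the total dose in mg given from Day 1 to Day 364, or to the end of treatment if that is earlier, divided by the item 7 duration of use. Numerator and divisor then cover the same days, in line with 2.3 items 27 and 31. For patients treated through Day 364 the item 7 duration equals 364 less rest days, so their values do not change.

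The cost is one sentence and the matching derivation in the analysis program. The SAP already defines both components, so no new data are needed.
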